10.2.3 Supply, Receipt, and Storage

Hiltonol® will be supplied by Oncovir to Duke's ICS. Hiltonol® is normally shipped or stored refrigerated at about 40°F (2-10°C), but should NOT be frozen. Based on extended formal stability data at +5°C ± 3°C and at +25°C ± 2°C, it is justified to accept temperature excursions during transport, shipment and storage of Hiltonol® at clinical sites up to +27°C for up to 72 hours. Likewise, temperature deviations between 0°C and +2°C are acceptable and have no effect on product quality.

10.2.4 Dispensing and Preparation

Patients will be provided Hiltonol®-only injections at the Day 84 visit to be self-administered at home every 2 weeks (±2 days) until the Day 140 visit. Patients will be provided their Hiltonol®-only injections on ice and instructed to store the vials immediately in their refrigerator (not freezer) once they arrive home. Patients or patients' caregivers will be trained to administer the Hiltonol® injections by the research nurse or other qualified designee at or prior to the Day 84 visit and will be provided with educational materials to take home (please see Section 18.1 Appendix A: Hiltonol Patient Administration Guide).

10.2.5 Compliance and Accountability

Hiltonol® will be stored in Duke ICS. The products will be signed out and distributed according to ICS SOPs. Study personnel are trained to use safe medication practices to reduce the risk of medication errors and AEs. Investigational drugs are stored separately from other drugs in an area of limited access and in accordance with special storage requirements. They are clearly labeled with the identity of the study drug and other control numbers.

Drug accountability records will be maintained for all clinical trial supplies. All empty and partially used clinical trial supplies will be destroyed in accordance with institutional guidelines. ICS will maintain detailed documentation of the receipt and/or destruction of the study agent. All materials coming in contact with the study agent including the syringe and needles will be disposed of as biological waste in the treatment room.

Patients will be provided a paper diary to document the dates of Hiltonol® home administration between the Day 84 visit and Day 140 visit. Patients will be asked to return the completed diary and any unused Hiltonol® to the clinic at their Day 140 visit (please see Section 18.2 Appendix B: Hiltonol Patient Diary).

10.2.6 Disposal and Destruction

Unused study drugs will be destroyed per institutional guidelines. Patients will also be provided a biohazard sharps container. Patients will dispose of used sharps in this biohazard sharps container and will bring it back to the clinic at their Day 140 visit for final disposal.

11 SUBJECT ELIGIBILITY

11.1 Inclusion Criteria

1. Age ≥ 18 years of age
2. Newly diagnosed IDH wild type (CARIS result), MGMT promoter unmethylated (CARIS result) WHO grade 4 glioma (e.g., GBM or high grade glioma with molecular features of GBM) with definitive resection prior to enrollment and residual radiographic contrast enhancement on immediate post-surgical computed tomography (CT) or magnetic resonance imaging (MRI).
3. CMV positive or negative by Immunoglobulin G (IgG) testing.
4. Karnofsky Performance Status (KPS) of $\geq 70\%$.
5. Hemoglobin ≥ 9.0 g/dl, absolute neutrophil count (ANC) $\geq 1,000$ cells/ μ l, platelets $\geq 100,000$ cells/ μ l.
6. Serum creatinine ≤ 3 x the upper limit of normal (ULN), serum glutamic oxaloacetic transaminase (SGOT) ≤ 3 times ULN
7. Bilirubin ≤ 1.5 times ULN (*Exception: Patient has known Gilbert's Syndrome or patient has suspected Gilbert's Syndrome, for which additional lab testing of direct and/or indirect bilirubin supports this diagnosis. In these instances, a total bilirubin of ≤ 3.0 x ULN is acceptable.*)
8. Signed informed consent approved by the IRB.
9. Patients must not be pregnant or breast-feeding. Patients of childbearing potential (defined as < 2 years after last menstruation or not surgically sterile) must use a highly effective contraceptive method (allowed methods of birth control, [i.e. with a failure rate of $< 1\%$ per year] are implants, injectables, combined oral contraceptives, intra-uterine device [IUD; only hormonal], sexual abstinence or vasectomized partner) during the trial and for a period of > 6 months following the last administration of trial drug(s). Patients with an intact uterus (unless amenorrhea for the last 24 months) must have a negative serum pregnancy test within 48 hours prior to first vaccination.
10. Patients that are able to produce sperm must agree to use a highly effective contraceptive method (allowed methods of birth control [i.e. with a failure rate of $< 1\%$ per year] include a partner using implants, injectables, combined oral contraceptives, IUDs [only hormonal], sexual abstinence or prior vasectomy) during the trial and for a period of > 6 months following the last administration of trial drug(s).

11.2 Exclusion Criteria

1. Patients with known potentially anaphylactic allergic reactions to gadolinium-diethylenetriaminepentaacetic acid (DTPA), or any component of the tetanus-diphtheria vaccine.

2. Patients with evidence of tumor in the brainstem, cerebellum, or spinal cord, radiological evidence of multifocal disease, or leptomeningeal disease.
3. Areas of high-grade glioma outside the original radiation field on the post XRT/TMZ MRI.
4. Patients who cannot undergo MRI.
5. Severe, active comorbidity, including any of the following:
 - Unstable angina and/or congestive heart failure requiring hospitalization;
 - Transmural myocardial infarction within the last 6 months;
 - Acute bacterial or fungal infection requiring intravenous antibiotics at the time of first vaccination;
 - Active infection requiring intravenous treatment or having an unexplained febrile illness ($T_{max} > 99.5^{\circ}\text{F}/37.5^{\circ}\text{C}$)
 - Chronic obstructive pulmonary disease exacerbation or other respiratory illness requiring hospitalization or precluding study therapy;
 - Known hepatic insufficiency resulting in clinical jaundice and/or coagulation defects;
 - Known immunosuppressive disease or Human Immunodeficiency Virus (HIV) and Hepatitis C positive status;
 - Major medical illnesses or psychiatric impairments that, in the investigator's opinion, will prevent administration or completion of protocol therapy;
 - Active connective tissue disorders, such as lupus or scleroderma that, in the opinion of the treating physician, may put the patient at high risk for radiation toxicity.
6. Co-medication that may interfere with study results (e.g., immuno-suppressive agents other than corticosteroids).
7. Patients who require corticosteroid doses that cannot be reduced to a dose ≤ 2 mg dexamethasone per day or equivalent at the time of first vaccination. Exceptions include nasal or inhaled steroid.
8. Prior, unrelated malignancy requiring current active treatment with the exception of cervical carcinoma *in situ* and adequately treated basal cell or squamous cell carcinoma of the skin. (Treatment with tamoxifen or aromatase inhibitors or other hormonal therapy that may be indicated in prevention of prior cancer disease recurrence, are not considered current active treatment.)
9. Patients are not permitted to have had any other conventional therapeutic intervention other than surgery, steroids, and 3-6 weeks of standard of care XRT with or without concomitant TMZ prior to enrollment.
10. Patients who received previous inguinal lymph node dissection or had radiosurgery, brachytherapy, or radiolabeled monoclonal antibodies to treat a central nervous system (CNS) tumor will be excluded.
11. Current, recent (within 4 weeks of the administration of this study agent), or planned participation in an experimental drug study.
12. Known history of autoimmune disease (with the exceptions of medically-controlled hypothyroidism and Diabetes Mellitus).

12 SCREENING AND ON-STUDY TESTS AND PROCEDURES

Table 3: Schedule of Events and Interventions

Description	Screening Period		Treatment Period						
	Post-XRT/TMZ		Priming Phase					Booster phase	
Vaccine	CMV screening	Final screening	#1	#2	#3	#4	#5	#6	#7
Day		At least one week post Td booster	1	4 (±1 days)	8 (±1 days)	15 (±2 days)	22 (±2 days)	84 (±7 days)	140 (±7 days)
General Evaluations									
CMV consent	X								
Main study consent		X							
Physical Exam ¹	X	X	X	X	X	X	X	X	X
Neurologic Exam ¹	X	X	X	X	X	X	X	X	X
Performance Status ¹	X	X	X	X	X	X	X	X	X
MMSE ¹			X						
AEs			Continuous						
Laboratory Evaluations									
Tetanus immunization booster	X								
CMV screen	X								
HLA-A*0201 status ²	X								
IDH mutation status ²	X								
MGMT promoter methylation status ²	X								
CBC w differential	X ³	X ³	X ³	X ³	X ³	X	X	X	X
CMP	X ³	X ³	X ³	X ³	X ³	X	X	X	X
Beta HCG ⁴	X	X							
Whole blood for immune analysis ⁵			X				X	X	X
CRS Blood Draws ⁶			X					X	X
Tissue Collection (archival or on-study) ⁷	Continuous								
Disease Evaluations									
MRI	X						X	X	X
Treatment									
P30-EPS Vaccine with vitals ⁸			X	X	X	X	X	X	X
Hiltonol [®] - only injection ⁹								Every 2 weeks at home (±2 days)	
Bevacizumab 7.5mg/kg IV q 3 weeks			AS NEEDED PER PHYSICIAN DISCRETION ¹⁰						

¹ Clinical evaluations will include a general physical examination, neurologic examination, and KPS. MMSE will only be assessed once – at the vaccine #1 visit prior to vaccine administration. During screening, the physical exam, neuro exam, and KPS should be assessed to confirm eligibility and will need to be repeated if not performed within 1 week of vaccine #1 administration.

² Testing will be performed on surgical specimen. May be obtained prior to enrollment on study as part of standard of care evaluation.

³ CBC w/diff and CMP needs to be drawn and resulted showing results suitable for eligibility as close as possible (within one week) prior to vaccine #1 administration. In some cases, CBC w/diff and CMP may be drawn as part of standard of care prior to the signing of main consent. The CMP will not be repeated if results meet eligibility and are within one week prior to vaccine #1; however, the CBC w/diff will need to be repeated if drawn more than 24 hours prior to vaccine #1 administration. CBC w/diff and CMP at Day 4 and/or Day 8 are not needed if they were already drawn for vaccine #1 or vaccine #2 within the same Monday through Friday “week.”

⁴ Beta HCG (quantitative) to be collected/resulted within 48 hours prior to vaccine #1 administration.

⁵ Blood draws for immune analysis on days with vaccination should be performed before vaccine administration. Whole blood for immune analysis containing 9 yellow top ACD 8.5 mL tubes and 2 red top 10 mL tubes will be drawn prior to vaccines #1, #5, #6, and #7. For subjects who complete all study vaccines without progressing, an attempt will be made to obtain blood for immunologic monitoring 2-3 times per year at standard PRTBTC clinic visits and at progression (whichever comes first). If a patient progresses at any other vaccine visit, an attempt will be made to obtain the blood for immune analysis.

⁶ Blood will be drawn at 2 hours (+15 minutes) after vaccines #1, #6, and #7 (2 10mL red top tubes) and will be sent to the designated lab for processing. Any blood draws occurring within the window of 2 hours (+15 minutes) will not be considered a deviation. Blood draws taking place outside of the window will be considered a deviation, and the reportability will be determined by the PI.

⁷ We will request archival tumor tissue from patients' baseline surgical resection or prior biopsy, as well as tumor tissue from any future surgeries that patients may undergo while on-study.

⁸ It will not be considered a deviation if the vitals are not captured exactly at the 30-minute time mark. As long as the patient is monitored for the protocol-specified amount of time, and as long as the correct number of sets of vitals have been collected for that time period, the patient will be considered sufficiently monitored. See Section 10.1.4 regarding the vitals schedule prior to and after each vaccine administration.

⁹ Patients will be contacted and/or sent a reminder (phone, email, or MyChart) by a study team member prior to each injection at home to help ensure that these doses are not missed.

¹⁰ Please refer to Sections 9.1 and 9.1.5.

12.1 Screening Examination

If patients are considered to be a potential candidate prior to XRT, the study may be mentioned to the patient, however, initial screening examination will take place at a Duke PRTBTC clinic visit after standard of care XRT/TMZ. If the patient wishes to pursue the study after XRT/TMZ, they will sign the CMV screening consent and then have blood drawn for CMV IgG testing per the Duke clinical lab requirements. The patient will also receive a tetanus booster after signing the screening consent.

All patients will need IDH and MGMT promoter methylation confirmed for eligibility purposes. These tests will need to be performed via standard of care practices, and the results will need to be available before the patient can commence study treatment. HLA status will be extracted from the electronic medical records. All HLA types are eligible in this study that focuses on safety and feasibility. However, we may restrict accrual to patients with a positive HLA-A*0201 status in subsequent future trials.

During collection of tumor sample at initial resection at Duke University, primary tissue will be banked and stored for assays, and slides will be sent for IDH-1/2 mutation analysis. For subsequent partitioning of pathology slides, tissue will be stored in formalin-fixed blocks. If the initial resection was not performed at Duke, all previously collected tissue specimens will be reviewed by Duke pathologists. MGMT gene promoter methylation and IDH mutation status will be determined using validated testing from CARIS. Even if MGMT gene promoter methylation status has already been determined outside of Duke, the test needs to be repeated by CARIS for determining eligibility. For patients where tumor resection was performed outside of Duke, tumor tissue is requested from the external hospitals as part of standard practice and will be sent directly to CARIS for MGMT gene promoter methylation. If the results of testing by CARIS are indeterminate, the results will be considered methylated and the patient will not be eligible for the study. We will also request archival tumor tissue from patients' baseline surgical resection or prior biopsy, as well as tumor tissue from future surgeries, but only in the case that the patients may undergo other clinically indicated biopsy or tumor resection while participating in this study. Further details on tissue processing are available in the ETAPA correlative laboratory manual. Available tumor tissue will be analyzed by correlative analyses as outlined in Section 9.3.

All patients will undergo a final screening visit after XRT/TMZ (at least one week post tetanus booster), in order to confirm eligibility and start vaccinations. Final screening visit tests will consist of a physical and neurological exam, performance status testing, CMV testing (if not already known), CBC with differential, CMP, and Beta HCG quantitative (if applicable). The post XRT/TMZ standard of care MRI will be used to confirm eligibility, unless a new scan is requested by the treating physician.

Once the final screening visit is complete and the patient is confirmed eligible, the study vaccinations should commence that day or the following day. If study vaccines do not start within one week of the final screening visit, the CMP and clinic visit (physical/neuro exam and KPS) will need to be repeated. The CBC w/diff needs to be

collected within 24 hours prior to vaccine #1. Mini-Mental Status Examination (MMSE) and blood for immune monitoring will also be drawn (9 yellow 8.5 mL ACD tubes and 2 red 10 mL tubes) once the patient is deemed eligible and just prior to vaccine #1.

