		
15.5, 15.5.1, 15.5.1.2). Definition of dose-limiting toxicity added (Sections 9.1.2, 12.5.3, 15.5.1.1). Added staggering of patients in initial dose level within each stratum (Sections 9.1.1, 15.5.1). Clarify 2 cohorts will be evaluated separately for the primary endpoint (Sections 5.3, 8, 9.1, 15.1, 15.5, 15.5.2). Increase in sample size (Sections 5.3, 9.1, 15.1, 15.5.1.3, 15.9). Update management of toxicities (Section 9.1.4). Updates to P30-EPS packaging/labeling (Sections 10.1.2, 15.1). Clarify antihistamine use (Section 12.6.3). Clarify details of secondary objective statistical analyses (Section 15.6). Add language regarding NSR determination of IVDs and IVD reporting (Sections 12.1.1, 12.1.2, 13.3). PRMC updates: Updates to P30-EPS vaccine label (Section 10.1.2). Additional information added regarding P30-EPS storage conditions (Section 10.1.3). New language regarding Hiltonol Patient Administration Guide (Section 10.2.2). Correction made to the Schedule of Events (Table 2).

Amended version 3.0:	4/5/2022	
Amended version 4.0	12/21/2022	
The eligibility requirement regarding tumor size and HLA A*0201 positive status have been removed (see Section 11.1). Tumor size limits are not needed for this study of safety and feasibility. While HLA status is of interest, we will not exclude patients based on it. Information potentially will inform future studies. This change also affects Sections 5.1, 7.2.2, Table 3, Footnotes Error! Bookmark not defined., Error! Bookmark not defined., and Error! Bookmark not defined., and Sections 12.1, 13.3, and 15.1. The section regarding HLA testing has been removed. In addition, we have removed the section recommending the avoidance of antihistamines. The volume of P30-EPS vaccine peptides was changed from 0.7 mL to 0.9 mL (Section 10.1.2).

Amended version 5.0	5/18/2023	
Study Drug Section 10 revised to correct the net peptide concentration of the P30-EPS drug product based on a change to the drug product specification.

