In order to provide this necessary CD4⁺ T cell help at priming, this trial will link the tetanus derived universal class II-binding P30 epitope to minimal HLA-A*0201-restricted class I binding TAA peptides. P30 (TT₉₄₇₋₉₆₇) has an extensive safety profile as it is a routine part of childhood vaccination. P30 is known to promiscuously bind human class II molecules and is a well-established CD4⁺ T cell helper epitope that boosts the immunogenicity of vaccination [26]. In this study, minimal class I epitopes restricted to HLA-A*0201 from three TAAs will be used- Ephrin type-A receptor 2 or EphA2 (TLADFDPRV) [27], *Cytomegalovirus* (CMV) pp65 (NLVPMVATV) [28, 29], and the survivin epitope (ELTLGEFLKL) [30]. Each of these peptides will be individually linked with a furin cleavage site (RVKR) to the P30 sequence (FNNFTVSFWLRVPKVSASHLE).

P30-EphA2 is a 34 amino acid synthetic peptide with the following sequence:
TLADFDPRVRVKRFNNFTVSFWLRVPKVSASHLE

P30-pp65 is a 34 amino acid peptide with the following sequence:
NLVPMVATVRVKRFNNFTVSFWLRVPKVSASHLE

P30-Survivin is a 35 amino acid peptide with the following sequence:
ELTLGEFLKLRVKRFNNFTVSFWLRVPKVSASHLE

Peptides will be mixed with carboxymethylcellulose, polyinosinic-polycytidylic acid (poly I:C), and poly-L-lysine double-stranded RNA (poly-ICLC) prior to injection, as has been safely used in other peptide vaccine trials in patients with glioma [27, 31]. Poly I:C and its clinical equivalent poly-ICLC (Hiltonol®), are TLR3 agonists responsible for inducing expression of inflammatory cytokines including IFN α , TNF α , and IL-6, which potentiates both antigen presentation by DCs and CD8⁺ T cell responses [32]. Peptides will be produced by BaChem (Torrence, CA), which routinely produces peptides of this length with 95% purity under Good Manufacturing Practice (GMP) conditions (BaChem, Personal Communication). Peptides will be pooled for administration.

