resolved with non-prescription analgesics within 8 days. When given with the adjuvant PF03512676 in 18 CMV seropositive HLA-A*0201 positive patients undergoing hematopoietic stem cell transplantation, this peptide was safe, expanded CMV-specific T cells, and only one patient experienced an AE related to vaccination (Grade 1 fever) [58]. It is expected that the vaccine will be even safer in the HLA-A*0201 subjects who will be included in this trial.

EphA2

The EphA2_{883–891} (TLADFDPRV) epitope as a separate peptide has been used in several trials in patients with glioma [27, 31]. In one trial, over 70% of the HLA-A*0201 positive patients demonstrated EphA2-specific T cells after vaccination [27]. In this prior study, a synthetic peptide representing the same EphA2_{883–891} epitope was given with other peptides at a dose of 300 µg/peptide/dose via subcutaneous vaccinations in combination with 20 µg/kg intramuscular (i.m.) injections of poly-ICLC to HLA-A2⁺ adults with low grade glioma [27]. AEs included grade 1 and 2 injection site reactions (100%) and flu-like symptoms (fatigue, myalgias, fever, headache), which were usually limited to 48 hours after each vaccine and were controlled with acetaminophen or ibuprofen. Three patients developed grade 1 leukopenia and one patient developed a grade 3 fever after the seventh vaccine that resolved with a nonsteroidal anti-inflammatory drug the next day.

The same research group also gave the EphA2_{883–891} epitope as part of a similar TAA multi-peptide vaccine to HLA-A*0201 positive pediatric patients with newly diagnosed malignant brainstem and non-brainstem glioma [59]. Twenty-six patients were enrolled to receive the TAA vaccine that included the P2 epitope (TT_{830–845}) in Montanide ISA-51, in combination with 30 µg/kg i.m. injections of Hiltonol[®]. Vaccines were given three weeks apart for eight courses of vaccination followed with booster vaccination every six weeks. Toxicities were mild and included injection site reactions (100%), flu-like symptoms (92%), Grade 1 GI symptoms (31%), Grade 1 leukopenia (15.4%), and no Grade 3 or higher toxicities. Eleven children showed cellular immune responses to the EphA2 epitope after vaccination.

Survivin

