Prior studies of pp65 mRNA-loaded DC vaccine conducted at Duke in CMV seronegative patients using this technique showed a pp65-specific T cells response rate of 2.5%. If the true response rate among CMV seronegative patients treated with the P30-EPS vaccine is similar, the expected number of responders is 0. Tabulated below is the probability of observing 1 or more responders out of 12 CMV seronegative patients as a function of the true (and unknown) response rate. The probability of observing 1 or more responders will be greater if more than 12 CMV seronegative patients are evaluable for this endpoint.

True Response Rate	Probability of Observing 1 or more Responders
2.5%	0.26
5%	0.46
10%	0.72
15%	0.86
20%	0.93
25%	0.97
30%	0.99

15.6.2 Secondary Objective: Tumor Associated Antigens (EphA2 and survivin) After Priming Vaccination

Objective: To assess whether EphA2- and survivin specific polyfunctional T cells increase after priming vaccination with P30-linked EphA2 and survivin peptides

Analysis Set: All patients treated at the MTD who have day 1, day 22 and day 84 PBMCs collected

Outcome: For analyses associated with EphA2 and survivin, the mean fold increase in EphA2- and survivin-specific T cells between day 1 and day 22 and the mean fold increase between day 1 and day 84.

Hypothesis: Vaccination with EphA2 and survivin linked to P30 will increase the number of EphA2- and survivin-specific CD8⁺ polyfunctional T cells over baseline (pre-vaccine day 1).

Analysis Plan: A one-sample t-test will assess whether there is a significant mean fold increase in EphA2- and survivin-specific T cells between day 1 and day 22.

A similar analysis will explore the change between day 1 and day 84.

Power Analysis: Within the ERADICATE study (Pro00000580), the mean (SD) fold change in 3-function polyfunctionality among CMV seropositive patients is 1.93 (1.38). Assuming normality, there is >99% power to detect a similar increase in the fold change in EphA2-, and survivin specific T cells with 18 or more patients ($\alpha=0.05$).

If the MTD among CMV seropositive patients is different from the MTD for CMV seronegative patients, then these analyses may be conducted separately within the two strata.

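### The immunogenicity analyses in Sections 15.6.1–15.6.4 pool all HLA types, although the vaccine's class I epitopes are restricted to one HLA allele, and the power statements make no allowance for this

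*Combined protocol and SAP*

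**What the plan says.** **Mechanism.** Section 7.2 states: "In this study, minimal class I epitopes restricted to HLA-A*0201 from three TAAs will be used". Each epitope is joined to the P30 helper sequence. Section 7.2.2 adds that the linked pp65 peptide lacks the class II epitopes of the longer pp65 peptide used in the PERFORMANCE trial.

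**Eligibility.** Section 12.1 says "All HLA types are eligible in this study that focuses on safety and feasibility" and that subsequent trials may be limited to patients positive for the allele. The version history for amendment 4.0 gives the reasoning: "While HLA status is of interest, we will not exclude patients based on it".

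**Data capture.** Section 12.1 says "HLA status will be extracted from the electronic medical records". Table 3 also lists "HLA-A*0201 status" at screening, with a footnote that places the test on the surgical specimen.

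**Analysis.** Sections 15.6.1–15.6.4 hypothesise increases in antigen-specific CD8+ polyfunctional T cells. The sets are defined by dose (the MTD) and sample availability, and for pp65 also by CMV stratum. For EphA2 and survivin, Section 15.6.2 uses "All patients treated at the MTD who have day 1, day 22 and day 84 PBMCs collected". None of the four sections mentions HLA.

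**Power.** Section 15.6.1 gives 78% with at least 6 seropositive patients, and Section 15.6.2 gives more than 99% with 18 or more. Both use the ERADICATE fold change of 1.93 (SD 1.38) at alpha 0.05.

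**Leftover text.** Section 7.2.2 still reads: "It is expected that the vaccine will be even safer in the HLA-A*0201 subjects who will be included in this trial".

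**The concern.** A class I epitope restricted to one HLA allele is meant to be presented to CD8+ T cells by that allele. Patients without it would therefore be expected to mount a weaker targeted response, or none. Opening eligibility was a deliberate and explained choice for a safety study, and it is not questioned here. The gap is that Section 15.6 did not follow it: the tests average the targeted response over patients with and without the allele, and the power statements treat everyone as if they had the full effect.

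At stake is a misleading reading of the secondary results. A vaccine that works as designed in allele-positive patients could look weakly immunogenic or inactive in the pooled analysis. The trial would also have no planned analysis to inform the restriction to allele-positive patients that Section 12.1 contemplates for later trials.

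**Working it through.** **Inputs from the documents.** Mean fold change 1.93, SD 1.38, alpha 0.05 (15.6.1, 15.6.2). About 18 patients evaluable at Day 140 and two-thirds of MTD patients seronegative (15.9), so about 12 seronegative and 6 seropositive. The null value and the sidedness of the t-test are not stated.

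**Assumptions.** The documents give no allele share f; 0.75, 0.5 and 0.3 are shown. Positives have mean 1.93 and SD 1.38. Negatives show no change, with SD 0.25 to 1.38.

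**1. The plan's own powers.** Exact noncentral-t power, two-sided 0.05, with d = (1.93 − null)/1.38:
- Null 0: d = 1.399; power 0.7805 at n=6 and 0.9998 at n=18. These match the stated 78% and >99%.
- Null 1: d = 0.93/1.38 = 0.674; power 0.27 at n=6 and 0.77 at n=18.

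The stated figures therefore reproduce against a mean of 0, which is coherent only if 1.93 is an increase. If it is a ratio, no change is 1.

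**2. Dilution of the mean.**
- Increase scale: pooled mean = 1.93f, which is 0.97 at f=0.5 and 0.58 at f=0.3.
- Ratio scale: pooled mean = 1 + 0.93f, which is 1.47 at f=0.5 and 1.28 at f=0.3.

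**3. Power of the pooled test.** 60,000 simulated trials per setting, counting rejections towards an increase at two-sided 0.05. Ranges span the SD assumed for negatives.

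| Scale | n | All positive | f=0.75 | f=0.5 | f=0.3 |
|---|---|---|---|---|---|
| Increase, null 0, negatives at 0 | 6 | 0.78 | 0.43–0.45 | 0.15–0.20 | 0.04–0.10 |
| | 18 | >0.99 | 0.94–0.99 | 0.63–0.88 | 0.28–0.48 |
| Ratio, null 1, negatives at 1 | 6 | 0.27 | 0.14–0.17 | 0.05–0.09 | 0.02–0.06 |
| | 18 | 0.77 | 0.50–0.61 | 0.25–0.38 | 0.12–0.17 |

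If the null of 0 is kept while 1.93 is a ratio and negatives sit at 1, n=18 power stays at or above 0.945. That is not reassurance: such a test rejects even without any response.

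**4. Seronegative pp65 response.** P(at least 1 of 12) = 1 − (1 − p)^12 reproduces every row of the table in Section 15.6.1. If only positives respond, p is replaced by p × f:
- p = 30%: 0.99 becomes 0.86 (15% overall, f=0.5) or 0.68 (9%, f=0.3).
- p = 20%, f=0.5: 10% overall, so 0.93 becomes 0.72.
- p = 2.5% (the protocol's prior figure): 0.26 becomes 0.14 (f=0.5) or 0.09 (f=0.3).

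**5. Testing allele-positive patients only,** at about the expected number positive:

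| Set | Positive | Null 0 | Pooled, null 0 | Null 1 | Pooled, null 1 |
|---|---|---|---|---|---|
| 18 (EphA2, survivin) | 9 | 0.955 | 0.63–0.88 | 0.43 | 0.25–0.38 |
| | 5 | 0.65 | 0.28–0.48 | 0.21 | 0.12–0.17 |
| 6 (pp65, seropositive) | 3 | 0.29 | 0.15–0.20 | 0.11 | 0.05–0.09 |
| | 2 | 0.12 | 0.04–0.10 | 0.07 | 0.02–0.06 |

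The number positive will vary. Weighting the power for k positives by the Binomial(18, f) probability of k gives 0.92 (f=0.5) and 0.65 (f=0.3) for null 0, and 0.42 and 0.24 for null 1. At 18 patients the restricted test still does better than the pooled one.

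**The case against.** The strongest reply is that the trial's primary objective is safety, eligibility was opened on purpose, no go/no-go decision hangs on these tests, and Section 15.6 allows alternative analyses. This stands as far as severity goes. It does not close the gap, because the permission for alternatives is tied to violated distributional assumptions and robustness checks, and nothing there commits to using HLA.

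Four stronger readings are tempting, and the documents do not support them:

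- **Patients without the allele cannot respond.** No section says so. The outcomes are worded as antigen-specific T cells; only the hypotheses specify CD8+. Reduced or absent response is an inference from class I restriction.
- **Opening eligibility made sound power figures invalid.** The effect size comes from a pp65 dendritic-cell vaccine given with adoptive lymphocyte transfer, with no HLA selection mentioned. Assigning 1.93 to allele-positive patients is itself an assumption. The drop from >0.99 to 0.77 at n=18 comes from changing the null, not from HLA. The seronegative table remains arithmetically correct because it is indexed by the true rate; only the applicable row changes.
- **3+3 dose clearance is undermined.** The primary endpoint is DLT by stratum and dose in the population enrolled. Every patient receives Hiltonol and the universal helper epitope, so exposure relevant to toxicity is not confined to carriers of the allele.
- **HLA is used nowhere.** Section 15.7.2 uses each patient's HLA class I type for neoantigen prediction. The gap is in Sections 15.6.1–15.6.4.

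It is also fair that restriction leaves very few seropositive patients for pp65, and that complete HLA data are not assured when status is taken from records.

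**Conclusion.** The point holds as a should-fix. Sections 15.6.1–15.6.4 pool all HLA types and assume the full effect in every patient, although the targeted CD8+ response depends, on the protocol's rationale, on HLA-A*0201.

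With 30–50% positive and no change in negatives, n=18 power falls to about 0.28–0.88 (from >0.99, increase scale) or 0.12–0.38 (from 0.77, ratio scale). At n=6 it falls to 0.04–0.20 (from 0.78) or 0.02–0.09 (from 0.27). At 75% positive the loss is smaller. These figures rest on an allele share that the documents do not give, on no response in negatives, and on the borrowed effect size applying to positives. The direction is the same on both coherent scales; the size cannot be fixed from the documents.

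**What to change.** - In Sections 15.6.1–15.6.4, prespecify an analysis of allele-positive patients treated at the MTD. It should preferably be the main set for the CD8+ hypotheses, and at minimum a prespecified subgroup. Report all patients alongside, and allele-negative patients separately as an internal comparison.
- State how patients with unknown HLA status are handled, and reconcile Section 12.1 (medical records) with the Table 3 footnote (surgical specimen) on the source of the result.
- State the scale and null of each t-test, and restate power over a range of allele shares.
- Update the sentence in Section 7.2.2 that still assumes subjects with the allele.
- Optionally, add a descriptive toxicity table by HLA status.

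The cost is SAP wording, some extra tabulation and, where records are incomplete, a rule for missing status. The downside is small sets (about 5–9 of 18 for EphA2 and survivin, about 2–3 seropositive patients for pp65) and lower stated power. For pp65 in seropositive patients, restriction removes the dilution but does not restore useful power, so that result is better presented as descriptive.
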